#### Data collection

Data will be collected from each participant through an individually administered interview schedule. The structured interview tool, developed by the researchers, will be designed to gather both personal and clinical data relevant to the study. Personal data will include participants' age (in years), gender, and Body Mass Index (BMI), which will be calculated using the following equation:

$$\text{BMI} = \text{weight (kg)} / \text{height}^2 (\text{m}^2).$$

Weight will be measured in kilograms (kg) using a calibrated scale, with participants wearing minimal clothing and no shoes. Height will be measured in meters (m) using a stadiometer, with participants standing upright on a flat surface (neither slumping nor stretching), barefoot, and with their heels, shoulders, and the back of the head aligned vertically, looking straight ahead without tilting the head up or down [33, 34].

Clinical data will include:

Fasting Blood Sugar (FBS) in mg/dL,

Random Blood Sugar (RBS) in mg/dL, and

Glycated Hemoglobin (HbA1c) in percentage (%).

BMI, FBS, and RBS will be measured at four time points: baseline, and at one, two, and three months. HbA1c will be assessed at two time points: baseline and at three months.

#### Intervention Procedures

Participants will be equally divided into two groups: a study group and a control group, each comprising 40 individuals. Following the provision of informed consent, participants will be randomly assigned to either the study group—which will receive Fenugreek supplementation in addition to standard care—or the control group, which will receive standard care alone. Randomization will be performed using a computer-generated random number list to ensure unbiased allocation.

Due to the practical challenges associated with dietary interventions and the absence of placebo controls in this setting, blinding will not be feasible for participants or the researchers administering the intervention. Consequently, participants will be aware of their group assignments. Nonetheless, outcome assessors and data analysts will remain blinded to group allocation throughout the data collection and analysis phases to minimize detection and performance biases.

Participants in the study group will continue their prescribed anti-diabetic treatment and adhere to a standardized dietary plan, in addition to consuming Fenugreek seed powder (10 g in sachet form) daily before breakfast and dinner for a duration of three months. In contrast, the control group will receive only their prescribed anti-diabetic treatment while following the same dietary plan. To enhance adherence to the intervention, researchers will maintain weekly telephone contact with participants in the study group, emphasizing the importance of compliance with both the Fenugreek supplementation and dietary plan.

Upon completion of the three-month intervention, a comparative analysis will be conducted between the study and control groups to evaluate the impact of Fenugreek supplementation on obesity and hyperglycemia in adults with T2DM.

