#### Aim of the study

This study aimed to examine the impact of Fenugreek supplementation on obesity and hyperglycemia among diabetic adults in Hail city, Saudi Arabia

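### Weekly calls that reinforce the shared dietary plan go to the study group only, so the fenugreek effect is mixed with the effect of extra diet-adherence support

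*Protocol*

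**What the plan says.** All of the relevant text is in the Protocol, mainly under Intervention Procedures.

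- **Intended contrast.** The study group is the one "which will receive Fenugreek supplementation in addition to standard care"; the comparator is standard care by itself.
- **Diet.** Study-group participants keep their prescribed treatment and "adhere to a standardized dietary plan, in addition to consuming Fenugreek seed powder". By contrast, "the control group will receive only their prescribed anti-diabetic treatment while following the same dietary plan". The diet is thus a background element common to both arms.
- **Calls.** To support adherence, the researchers are to keep up "weekly telephone contact with participants in the study group, emphasizing the importance of compliance with both the Fenugreek supplementation and dietary plan".
- **Blinding.** There is no placebo, and "blinding will not be feasible for participants or the researchers administering the intervention". Outcome assessors and analysts are to be blinded, and the protocol expects this to limit performance bias as well as detection bias.
- **Attribution.** The stated aim is to "examine the impact of Fenugreek supplementation on obesity and hyperglycemia among diabetic adults". The final comparison of the groups is "to evaluate the impact of Fenugreek supplementation on obesity and hyperglycemia in adults with T2DM". Both research hypotheses likewise contrast people who take fenugreek with people who do not.

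The outcomes under Data collection are BMI, FBS and RBS at baseline and at one, two and three months, and HbA1c at baseline and three months. No measure of dietary adherence is listed.

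**The concern.** A two-arm comparison isolates fenugreek only if everything else is handled alike in both arms. Here the diet is prescribed alike but not supported alike: one arm is reminded of it every week by a researcher and the other, as written, is not. All four outcomes respond to how well people keep to a diet. If the reminders work at all, they lower weight and glucose in the study group, which is the direction the hypotheses predict.

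The calls coincide completely with the fenugreek arm. Every participant offered fenugreek is called and no other participant is, so no analysis of the trial data can separate the two effects. With no adherence data, the report could not even show whether diet adherence differed between the arms. The main conclusion of the trial is at stake: a positive result would have a second, plausible explanation that could not be ruled out.

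**Working it through.** **1. What each arm receives (Intervention Procedures)**

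| Component | Study group | Control group |
|---|---|---|
| Prescribed anti-diabetic treatment | yes | yes |
| Standardized dietary plan | yes | yes, the same plan |
| Fenugreek powder | yes | no |
| Weekly call on fenugreek compliance | yes | none described |
| Weekly call on diet compliance | yes | none described |

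The third and fourth rows can be defended as fenugreek and its delivery. The fifth cannot, because it acts on something both arms are meant to have equally.

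**2. Form of the bias**

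Let F be the effect of fenugreek and C the effect of the calls through diet adherence and added attention. If the two add, the expected difference between arms is F + C. A test of zero difference is then a test of F + C = 0, although it is reported as a test of F = 0.

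**3. Inputs for an illustration**

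- 40 per arm (Intervention Procedures).
- 5% significance level and Student's t-test for two independent groups (Statistical analysis). Sidedness is not stated; two-sided is assumed.
- F = 0, so that any significant result is a false fenugreek finding.
- C is not in the documents. The Sample size section cannot supply it, because that calculation is for the precision of one proportion: n0 = 1.96² × 0.5 × 0.5 / 0.1² = 96.04, and 96.04 / (1 + 95.04/416) = 78.2. This reproduces the stated 78 but contains no SD and no effect size. C is therefore assumed to lie between 0.1 and 0.5 SD.

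**4. Calculation**

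Noncentrality δ = C / √(2/40) = C / 0.2236, with 78 degrees of freedom and critical value 1.991. Rejection probabilities come from the noncentral t distribution.

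| Assumed C (SD) | δ | Significant, either direction | Significant, favouring the study group |
|---|---|---|---|
| 0 | 0 | 5.0% | 2.5% |
| 0.1 | 0.447 | 7.3% | 6.4% |
| 0.2 | 0.894 | 14.3% | 14.1% |
| 0.3 | 1.342 | 26.3% | 26.3% |
| 0.5 | 2.236 | 59.8% | 59.8% |

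**5. Would a larger trial help?**

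No. With 80 per arm and C = 0.2 SD, δ = 0.2 / √(2/80) = 1.265 and the two-sided rejection rate rises from 14.3% to 24.2%. The bias stays the same while the precision improves.

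**6. Call volume**

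Taking three months as 13 weeks:

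- Present plan: 40 × 13 = 520 calls.
- Weekly calls to everyone: 80 × 13 = 1,040, which is 520 more.
- Calls every two weeks to everyone: 80 × 6.5 = 520, the same as now.

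**The case against.** The strongest defence is that the calls belong to a pragmatic package: they are introduced to support adherence, and the trial could be read as testing fenugreek with telephone support against usual care. That reading covers calls about sachet intake. It does not cover the dietary message, since the diet belongs to both arms, and the aim, the hypotheses and the final comparison all name fenugreek alone.

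Several narrower points stand and limit how the concern should be put:

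- The protocol does not say outright that controls get no calls. This is inferred from the calls being assigned to the study group and from the word describing controls as receiving only their treatment. It is the natural reading, and nothing elsewhere contradicts it.
- The text describes contact that stresses compliance, not dietary counselling. Reminders are a weaker co-intervention than coaching.
- The size of the call effect is unknown, and its favourable direction is likely but not shown in the documents. At 0.1 SD the excess over the nominal rate is small; the 60% figure depends wholly on choosing 0.5 SD.
- Simple addition of the two effects is itself an assumption.

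Two other defences fail. Randomisation balances participants at baseline, whereas the calls come after allocation. Blinded assessors protect against biased measurement, but better diet adherence truly changes weight and glucose, so a blinded assessor would record the distorted value correctly. For the same reason, the protocol's expectation that assessor and analyst blinding limits performance bias is misplaced.

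**Conclusion.** The concern holds. As written, the trial compares fenugreek plus weekly diet-adherence reminders with neither, and then credits the difference to fenugreek. A between-group difference in BMI, FBS, RBS or HbA1c could not be attributed to fenugreek alone.

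This rests on the design and not on the percentages. The range of 7% to 60% false fenugreek findings, against a nominal 5%, illustrates what assumed call effects of 0.1 to 0.5 SD would do at 40 per arm with a two-sided test; the documents offer nothing to narrow it. The conclusion would change only if controls are in fact to receive equivalent calls, in which case the protocol must say so. The point must be fixed before recruitment, because the confounding is complete and cannot be undone in the analysis, whatever a statistical analysis plan may contain.

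**What to change.** **Preferred change.** Under Intervention Procedures, provide calls to both groups on the same timetable, with the same script on the dietary plan, and add an item on fenugreek intake for the study group only. Describe the control condition accordingly, since it would then be standard care with telephone diet support and no longer standard care alone. Record dietary adherence in both groups during the calls, so that any remaining imbalance is visible. Reword the blinding statement so that it claims protection against detection bias only.

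**Cost.** Weekly calls to everyone add about 520 short calls. Calling all 80 every two weeks adds none, but halves the frequency of adherence prompts in the study group.

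**Lesser options.**

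- Remove the dietary message from the study-group calls. This costs nothing and takes out the explicit diet component, but it leaves about 13 unmatched researcher contacts in an unblinded trial.
- Keep the calls as they are and restate the aim, hypotheses and conclusions as concerning fenugreek plus weekly adherence support against standard care. This is honest and free, but gives up the claim about fenugreek itself.

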#### Statistical analysis

The collected data will be carefully categorized, coded, computerized, tabulated, and will be analyzed using the Statistical Package for Social Sciences (SPSS) version 23 program. To explore the relationships between the study variables, cross-tabulation will be performed, which will be a standard and appropriate approach for identifying associations and distributions of categorical data.

Comparisons between groups of categorical variables will be conducted using the Chi-square test (Monte Carlo). This test will be particularly useful when expected frequencies will be low, and thus, its use here will be well-justified. For comparisons involving two categories of normally distributed quantitative variables, the Student's t-test will be employed, which will be the conventional choice for assessing mean differences between two independent groups.

Additionally, to compare the three repeated measurements (baseline, one, two, and three months) within each group, analysis of variance (ANOVA) with repeated measures will be conducted, followed by Bonferroni adjustment to control for multiple comparisons. The application of partial Eta squared will be appropriate for determining the effect size of the intervention, thus providing insights into the magnitude of observed differences. Throughout the analyses, a 5% significance

level will be used to judge the statistical significance of the results, aligning with the standard threshold in clinical research.

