## 2. Materials and Methods

### Study design

A quasi-experimental research design (pretest-posttest nonequivalent control group design) will be adopted in this study.

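### The only between-group test named for BMI, FBS, RBS and HbA1c is an unadjusted t-test, although a baseline is collected for each; against ANCOVA the precision lost runs from near zero to large

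*Protocol*

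**What the plan says.** The protocol's Statistical analysis section names three tests:

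- A chi-square test, for categorical variables.
- For normally distributed quantitative variables in two categories, Student's "t-test will be employed, which will be the conventional choice for assessing mean differences between two independent groups".
- Repeated measurements: "within each group, analysis of variance (ANOVA) with repeated measures will be conducted", followed by a Bonferroni adjustment.

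It then adds: "The application of partial Eta squared will be appropriate for determining the effect size of the intervention". No between-group model is named for that quantity to come from.

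The Data collection section supplies a baseline for every quantitative outcome: "BMI, FBS, and RBS will be measured at four time points: baseline, and at one, two, and three months" and "HbA1c will be assessed at two time points: baseline and at three months".

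The purpose is a between-group contrast. H1 and H2 compare those who take fenugreek with those who do not, and Intervention Procedures promises that "a comparative analysis will be conducted between the study and control groups to evaluate the impact of Fenugreek supplementation on obesity and hyperglycemia".

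On allocation, Intervention Procedures states: "Randomization will be performed using a computer-generated random number list to ensure unbiased allocation". The Study design section instead describes a "pretest-posttest nonequivalent control group design".

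**The concern.** The baselines are collected but enter no test that compares the groups. The repeated-measures ANOVA does use them, but only inside each arm, and a within-arm change does not answer H1 or H2. That leaves an unadjusted t-test to carry both hypotheses with 40 participants per arm.

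The t-test sentence names no variables. That it covers BMI, FBS, RBS and HbA1c is an inference: they are the only quantitative outcomes listed under Data collection.

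At stake is precision. An interval wider than the collected data allow makes a real effect easier to miss. How much is lost depends on two things the protocol does not state: whether the test uses 3-month values or changes from baseline, and how strongly baseline and 3-month values correlate.

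**Working it through.** **The plan's own figure.** The Sample size section uses N = 416, p = 0.5, margin d = 0.10 and 95% confidence:

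n = N·p·q / [(d/1.96)²·(N − 1) + p·q] = 104 / (1.080 + 0.25) = 78.2

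This reproduces the stated 78, later raised to 80. It is the precision of one proportion. It contains no SD, difference, power or correlation from which the precision of a mean difference could be derived.

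**Inputs.** From the protocol: 40 per arm and a 5% significance level. Assumed: a two-sided test, equal variances at both visits, and a baseline to 3-month correlation r of 0.3 to 0.9.

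**Effective SD of the comparison** (σ = SD of the outcome):

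- t-test on 3-month values: σ
- t-test on changes: σ·√[2(1 − r)]
- ANCOVA: σ·√(1 − r²)

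The confidence-interval width relative to ANCOVA is therefore 1/√(1 − r²) for 3-month values and √[2/(1 + r)] for changes. The n per arm needed to match ANCOVA with 40 is 40/(1 − r²) and 80/(1 + r) respectively, rounded up. For example, at r = 0.7: 1/√0.51 = 1.40 and √(2/1.7) = 1.08; 40/0.51 = 78.4, so 79, and 80/1.7 = 47.1, so 48.

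| r | CI width, 3-month | CI width, change | n to match, 3-month | n to match, change |
|---|---|---|---|---|
| 0.3 | 1.05 | 1.24 | 44 | 62 |
| 0.5 | 1.15 | 1.15 | 54 | 54 |
| 0.7 | 1.40 | 1.08 | 79 | 48 |
| 0.9 | 2.29 | 1.03 | 211 | 43 |

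A simulation of 20,000 trials with 40 per arm gave mean width ratios of 1.04, 1.15, 1.39, 2.28 (3-month) and 1.23, 1.15, 1.08, 1.02 (change). Under random allocation, type I error was 0.046 to 0.053 for all three tests.

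**Difference detectable with 80% power**, in SD units (noncentral t, 78 df; 77 for ANCOVA):

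| r | 3-month | change | ANCOVA |
|---|---|---|---|
| 0.3 | 0.63 | 0.75 | 0.61 |
| 0.5 | 0.63 | 0.63 | 0.55 |
| 0.7 | 0.63 | 0.49 | 0.45 |
| 0.9 | 0.63 | 0.28 | 0.28 |

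**BMI illustration.** Power for an assumed difference of 1 kg/m², with the SD running from 3 to 6 kg/m²:

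| r | 3-month | change | ANCOVA |
|---|---|---|---|
| 0.7 | 31% to 11% | 48% to 16% | 54% to 18% |
| 0.9 | 31% to 11% | 91% to 38% | 92% to 39% |

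**If allocation were not random.** Take a baseline gap of 0.5 SD, no treatment effect and r = 0.7.

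- If each group stays at its own mean, the false difference is 0.50 SD (3-month), 0.50 − 0.50 = 0 (change) and 0.50 − 0.7 × 0.50 = 0.15 (ANCOVA).
- If everyone regresses to one common mean, it is 0.7 × 0.50 = 0.35, 0.35 − 0.50 = −0.15, and 0.35 − 0.35 = 0.

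No one method is safe in both cases.

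**The case against.** The strongest reply is that nothing here is invalid. Under randomisation the t-test holds its type I error, and covariate adjustment is often left to an analysis plan, which is not at hand. That would carry weight if the protocol were silent. It is not: it selects a test and defends it as conventional, so an analysis plan using ANCOVA would depart from the protocol.

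The second reply is about size, and much of it stands. The ratio of 2.29 and the 211 per arm apply only to 3-month values at a correlation of 0.9. At that correlation a t-test on changes is only 1.03 times as wide. The better of the two t-tests is never more than 1.15 times as wide as ANCOVA at the correlations computed, so 2.29 should not be read as the expected loss. But choosing the better t-test requires knowing the correlation, and the protocol does not say which quantity is tested. ANCOVA removes the need to choose.

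It is also fair that the t-test sentence could be meant for baseline characteristics such as age. In that case the protocol names no between-group test for its outcomes at all, and the same new sentence is needed.

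Three further points are true but separate: ANCOVA does not repair the sample size, H2 spans several glycaemic measures with no rule for a split result, and the month 1 and month 2 values stay outside the between-group comparison. None of them weakens the case for adjusting for baseline.

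**Conclusion.** The concern holds. As written, the protocol compares the arms without using the baselines it collects. Relative to ANCOVA, the interval is 1.05 to 2.29 times as wide if 3-month values are tested and 1.24 down to 1.03 times as wide if changes are tested, as the correlation goes from 0.3 to 0.9. Those figures rest on assumed correlations and equal variances at the two visits.

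This is a loss of precision, not of validity, provided that allocation is random as Intervention Procedures says. If the label in Study design were the true one, the comparison could also be biased, and baseline adjustment alone would not remove that. The change should be made but is not critical: the gain may be small, and the sample size stays weak either way.

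**What to change.** In Statistical analysis, replace the t-test for the between-group comparison of BMI, FBS, RBS and HbA1c with wording such as:

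> *Each outcome will be compared between groups at three months by ANCOVA, with group and the baseline value of the same outcome as terms. The adjusted difference and its 95% confidence interval will be reported, and H1 and H2 will be judged on this result.*

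Take any partial eta squared reported as the effect size of the intervention from the group term of this model. Reconcile the Study design section with Intervention Procedures, so that the protocol states one method of allocation.

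The cost is wording only, in Statistical analysis and in whichever of the two allocation passages is changed. No new data or visits are needed, and SPSS, the package already named, can run ANCOVA.

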#### Sample size

---

The Epi Info 7 statistical program were used to estimate the appropriate sample size for this study, based on the following parameters: a population size of 416 participants per month, an expected frequency of 50%, a margin of error of 10%, and a confidence level of 95%. According to these calculations, the minimum required sample size is determined to be 78 participants. To account for potential non-response and to ensure adequate representation, the final sample size will be increased to 80 participants.

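### The within-group repeated-measures ANOVA miscounts its measurements, cannot cover HbA1c as listed, uses complete cases only and does not test H1 or H2; a baseline-adjusted mixed model would do better at little cost

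*Protocol*

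**What the plan says.** The Statistical analysis section of the protocol describes the within-group analysis as being "to compare the three repeated measurements (baseline, one, two, and three months) within each group". The method is "analysis of variance (ANOVA) with repeated measures will be conducted, followed by Bonferroni adjustment to control for multiple comparisons". No number of comparisons is given. Partial eta squared is then named as the measure of the intervention's effect size, and a 5% level applies throughout.

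The schedule is in the Data collection section: "BMI, FBS, and RBS will be measured at four time points: baseline, and at one, two, and three months". For the remaining outcome, "HbA1c will be assessed at two time points: baseline and at three months".

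The group comparison is a separate test. For normally distributed quantitative variables, "the Student's t-test will be employed, which will be the conventional choice for assessing mean differences between two independent groups". The Intervention Procedures section places the comparison of the two groups of 40 after the three months of intervention. Both research hypotheses (H1 on BMI, H2 on blood glucose) compare people who take fenugreek with people who do not.

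The Sample size section raises 78 to 80, giving as one reason "To account for potential non-response". It states no missed-visit rate.

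**The concern.** Four things about the ANOVA sentence are unsatisfactory.

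- **Count.** The word three disagrees with the four occasions listed beside it and with the Data collection section.
- **HbA1c.** An ANOVA over four occasions cannot be run on an outcome measured twice. It is the only within-group method named, yet the Expected Outcomes section anticipates a significant fall in HbA1c.
- **Complete cases.** Classical repeated-measures ANOVA in SPSS drops a participant from the analysis of an outcome if any one visit is missing. A missed month-1 glucose would also remove that person's month-2 and month-3 values from that ANOVA.
- **Question answered.** Testing change over time separately in each group does not test whether the groups differ. Both groups follow the same dietary plan, so change within the fenugreek group mixes any effect of fenugreek with diet and time.

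At stake are a clear specification, some precision in the within-group results, and an effect size (partial eta squared) that could be read as the effect of fenugreek when it describes change within one group. If missed visits relate to glucose control or tolerability, the within-group results could also be biased.

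**Working it through.** **1. The plan's own figure.** The only computed number is the sample size. With N = 416, p = 0.5, margin d = 0.10 and z = 1.96:

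n = N·p·q / [(d²/z²)(N − 1) + p·q] = 104 / [(0.01/3.8416) × 415 + 0.25] = 104 / 1.3303 = 78.2

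This reproduces the stated 78. It is a precision calculation for one proportion. It contains no power, effect size or attrition rate, so any missed-visit rate used below is an assumption.

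**2. Occasions and Bonferroni families.** Pairs among k occasions number k(k − 1)/2, and the threshold is 0.05 divided by the number of comparisons.

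| Reading | Occasions | Comparisons | Threshold |
|---|---|---|---|
| BMI, FBS, RBS: all pairs | 4 | 6 | 0.05/6 = 0.0083 |
| BMI, FBS, RBS: each follow-up against baseline | 4 | 3 | 0.05/3 = 0.0167 |
| The word three taken literally: all pairs | 3 | 3 | 0.05/3 = 0.0167 |
| HbA1c | 2 | 1 | 0.05 |

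The protocol does not say which family is meant.

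**3. Complete cases in the ANOVA.** Assume baseline is complete and each of the three follow-up visits is missed independently at rate q. The share with all four visits is (1 − q)³. The share with a month-3 value is 1 − q.

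| Assumed q | (1 − q)³ | Complete, of 40 | With month 3, of 40 |
|---|---|---|---|
| 2% | 0.941 | 37.6 | 39.2 |
| 5% | 0.857 | 34.3 | 38.0 |
| 10% | 0.729 | 29.2 | 36.0 |
| 15% | 0.614 | 24.6 | 34.0 |

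Independence matters. If the same people miss every visit, complete cases equal 40(1 − q), which is 38 at 5% and 36 at 10%. If no one misses more than one visit, they equal 40(1 − 3q), which is 34 and 28. The range is therefore 34 to 38 at 5% and 28 to 36 at 10%.

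**4. Where the loss falls.** The ANOVA is within group, so the loss affects the tests of change over time and the partial eta squared taken from them. A month-3 t-test between groups does not need months 1 and 2, so it keeps everyone in the last column of the table.

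**5. Match to the hypotheses.** H1 and H2 concern a difference between groups. The t-test addresses that. The ANOVA does not, because its monthly BMI, FBS and RBS data are analysed one group at a time. The planned group comparison therefore takes nothing from the repeated measurements that the trial collects.

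**The case against.** The strongest reply is that this is mostly clerical. The four occasions are listed, the Data collection section confirms them, and SPSS scales its pairwise Bonferroni output to the number of levels entered. That stands: the intended count is recoverable, and the practical ambiguity is limited to which contrasts are meant. Nor does the protocol say that the ANOVA is applied to HbA1c. The gap there is that no within-group comparison is named for its two values, while the t-test can still compare the groups on it.

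A second reply is that no section says incomplete participants are dropped, and that a rule for missing data may sit in a statistical analysis plan that is not shown. That also stands, and the absence of such a rule is no part of this point. What remains is narrower: the protocol itself names a method and a software package, and that method in its classical form uses complete cases only. Imputation beforehand is not ruled out.

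Two stronger readings are tempting, and the documents support neither.

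- A reader might carry the complete-case counts into the group comparison. With an assumed standardised difference of 0.634, power would then fall from 80% with 40 per group to 73% with 34 or 66% with 29. The group comparison is a separate t-test, and at month 3 it would keep 38 or 36 of 40. The effect size and the 80% starting power are not in the protocol either.
- A reader might infer that the familywise error exceeds 5%, because 0.05/3 used on all six pairs allows up to 6 × 0.0167 = 10% (about 8% in simulation). No section proposes that divisor for six pairs, and 0.05/3 is correct for three comparisons with baseline.

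The increase from 78 to 80 is likewise no evidence of under-provision for this ANOVA. It is a non-response allowance on a one-proportion calculation.

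**Conclusion.** The point holds as a cheap improvement. It does not show that the plan would give a wrong result.

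Three parts are certain from the text: the count contradicts itself and the schedule, the ANOVA as listed cannot be run on HbA1c, and the Bonferroni family is left open between six and three comparisons. That within-group tests do not address H1 and H2 follows from how the hypotheses are worded.

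The complete-case loss is conditional. It rests on how classical repeated-measures ANOVA behaves in SPSS and on missed-visit rates that the protocol does not give. At an assumed independent 5% or 10% per follow-up visit, about 34 or 29 of 40 per group would remain in the within-group analysis. The month-3 group comparison is not affected by this.

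The case for change is that a better method uses data already scheduled for collection and software already named, and answers the hypotheses directly.

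**What to change.** In the Statistical analysis section:

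- Write four measurements for BMI, FBS and RBS.
- Replace the within-group ANOVA for these outcomes with a linear mixed model (SPSS MIXED) on months 1 to 3, with group, visit, group by visit and the baseline value of the outcome, using all available visits. Name the month-3 group difference as the main contrast, and report it with its confidence interval in place of a within-group partial eta squared.
- Analyse month-3 HbA1c by group, adjusted for baseline HbA1c.
- State the number of contrasts to which any Bonferroni correction applies.

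The mixed model keeps participants who miss a visit and is valid when missingness depends on observed data. It does not remove bias from visits missed for unrecorded reasons.

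The cost is a change of wording and slightly more analysis work. No new data, visits or software are needed.

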#### Research hypotheses

H1: Diabetic adults who consume Fenugreek supplementation exhibit less BMI will be compared to those who do not consume it.

H2: Diabetic adults who consume Fenugreek supplementation exhibit lower blood glucose levels will be compared to those who do not consume it.

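### Partial eta squared is labelled the effect size of the intervention, but the only ANOVA named runs within each arm, so a change shared by both arms could be reported as a fenugreek effect

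*Protocol*

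**What the plan says.** Research hypotheses (Protocol): both hypotheses are contrasts between fenugreek users and non-users. H2, for example, says that users "exhibit lower blood glucose levels will be compared to those who do not consume it"; H1 has the same form for BMI.

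Statistical analysis (Protocol): quantitative variables are compared between two groups by Student's t-test, described as "the conventional choice for assessing mean differences between two independent groups". The longitudinal analysis is to "compare the three repeated measurements (baseline, one, two, and three months) within each group, analysis of variance (ANOVA) with repeated measures", with Bonferroni adjustment. The sentence after that reads: "The application of partial Eta squared will be appropriate for determining the effect size of the intervention". No group factor, group-by-visit term or baseline-adjusted model is named anywhere.

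Intervention Procedures (Protocol): after three months "a comparative analysis will be conducted between the study and control groups to evaluate the impact of Fenugreek supplementation". On background care, "the control group will receive only their prescribed anti-diabetic treatment while following the same dietary plan"; the study group also continues its prescribed treatment.

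Data collection (Protocol): BMI and the two blood sugar measures are taken at four time points, but "HbA1c will be assessed at two time points: baseline and at three months".

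**The concern.** A repeated-measures ANOVA fitted inside one arm has a single factor, visit. Its partial eta squared is the share of that arm's within-person variation explained by visit. It responds to anything that moves the arm's mean over three months: fenugreek, the dietary plan, continued drug treatment, or simple drift. It cannot separate these, because no control data enter the calculation.

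The Protocol nevertheless names this kind of statistic as the size of the intervention effect. A 20 mg/dL fall in fasting glucose in the study arm gives the same partial eta squared whether fenugreek caused all of it, half of it or none. Both arms follow one dietary plan and stay on treatment, so a change in both arms is a plausible result here. The figure reported as fenugreek's effect would then not estimate the contrast stated in H1 and H2.

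**Working it through.** **Inputs from the Protocol.** 40 participants per arm (Intervention Procedures); four visits for BMI, FBS and RBS and two for HbA1c (Data collection); 5% significance level (Statistical analysis). The Protocol gives no value of partial eta squared, so there is no stated figure to reproduce.

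**Assumptions.** The Protocol gives no SD, correlation or expected change. For FBS the check uses SD 30 to 50 mg/dL, equal correlation between visits of 0.4 to 0.8, and the same linear fall D by month 3 in both arms, with D from 0 to 30 mg/dL. The true fenugreek effect is set to zero.

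**Formula.** Within one arm of n = 40 with 4 visits:

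- Partial eta squared = SS_time / (SS_time + SS_error).
- For a linear fall D, the visit means deviate from their average by D/2, D/6, −D/6 and −D/2. The squares sum to (5/9)D².
- Expected SS_time = 40 × (5/9) × D² + 3 × SD² × (1 − correlation).
- Expected SS_error = 3 × 39 × SD² × (1 − correlation).

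**Worked case: SD 40, correlation 0.6, D = 20.** SD² × (1 − correlation) = 1600 × 0.4 = 640.

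- SS_time = 22.22 × 400 + 3 × 640 = 8,889 + 1,920 = 10,809.
- SS_error = 117 × 640 = 74,880.
- Ratio = 10,809 / 85,689 = 0.126.
- With D = 0 the ratio is 1,920 / 76,800 = 0.025, which is the chance floor.

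**Simulation at SD 40, correlation 0.6** (5,000 trials per scenario; zero fenugreek effect):

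| Shared fall (mg/dL) | Study-arm partial eta squared | Control-arm | Group-by-visit |
|---|---|---|---|
| 0 | 0.025 | 0.025 | 0.013 |
| 10 | 0.05 | 0.05 | 0.013 |
| 15 | 0.08 | 0.08 | 0.013 |
| 20 | 0.125 | 0.125 | 0.013 |
| 30 | 0.23 | 0.23 | 0.013 |

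In these settings the within-arm ANOVA is significant in about 31%, 62%, 89% and over 99% of trials for falls of 10, 15, 20 and 30 mg/dL. The group-by-visit test and the month-3 two-sample t-test each reject in 4% to 6% of trials, whatever the shared fall. The group-by-visit value of 0.013 is its own chance floor: 3 / (3 + 234), where 234 = 6 × 39.

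**Range over the assumptions.** The low end is SD 50 with correlation 0.4, and the high end is SD 30 with correlation 0.8. Study-arm partial eta squared runs from 0.04 to 0.12 for a shared fall of 10, from 0.07 to 0.31 for a fall of 20, and from 0.12 to 0.49 for a fall of 30.

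**HbA1c.** With two time points the within-arm ANOVA is a paired t-test, and partial eta squared = t² / (t² + 39). For an assumed SD of 1.0 to 1.5 points, correlation 0.5 to 0.7 and a shared fall of 0.3 points, the mean is 0.06 to 0.15, against the same floor of 0.025.

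**The case against.** The strongest reply is that the Protocol never says which model supplies partial eta squared. The sentence speaks of the intervention, the hypotheses and the three-month evaluation are between-group, and an eta squared can be derived from a two-group comparison. On that reading the source is merely unspecified, and a statistical analysis plan could settle it. This is partly right: the link does rest on sentence order. But partial eta squared is customarily an ANOVA statistic, the sentence directly follows the only ANOVA named, and nothing ties it to the t-test. The Protocol chose the measure and stated what it measures, so this is more than a detail left for later.

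Second, the ANOVA is run in the control arm too, so a purely shared change would show as similar values in both arms beside a null t-test. That is true and would help a careful reader. It does not make either arm's value an intervention effect, and the Protocol does not say that the two will be compared.

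Third, no hypothesis test is harmed. This stands in full: the between-group t-test is valid, and a shared change does not inflate it.

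Fourth, the size depends on assumed inputs, and the top value of 0.49 needs a shared fall of one full SD with high correlation. That also stands, which is why the range is shown. The principle does not depend on the size.

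Two side remarks carry little weight. Regression to the mean is a weak explanation for glucose, because the entry criteria set no glycaemic threshold. The mismatch between the ANOVA's listed visits and HbA1c needs a clarifying phrase but is not central.

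**Conclusion.** The concern holds. Followed as written, and with partial eta squared taken from the only ANOVA named, the analysis would report as the size of the intervention effect a number that does not estimate it. With zero fenugreek effect, that number can rise from its floor of 0.025 to about 0.125 for a shared 20 mg/dL fall (0.07 to 0.31 over the assumed SDs and correlations), while the between-group quantity does not move. The SD, correlation, linear shape and size of fall are assumptions. That the control arm is absent from the statistic is not. The damage is confined to the effect size and its interpretation, so this should be fixed but does not undermine the planned test between arms.

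**What to change.** In the Statistical analysis section:

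- State that H1 and H2 are decided by the between-group comparison.
- Use one model per outcome with group, visit and group-by-visit terms, or a month-3 comparison adjusted for baseline. The latter also suits HbA1c with its two time points.
- Report the three-month between-group difference with its 95% CI as the effect size. If partial eta squared is kept, give it only for the group-by-visit term.
- Label the within-group ANOVAs as descriptive, and say how HbA1c is handled.
- Clerical: the sentence says three repeated measurements but lists four; correct the count.

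The cost is a few sentences of analysis wording. The planned data and the planned SPSS package suffice, with no extra visits or participants.
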